7 INVESTIGATIONAL MEDICINAL PRODUCT

Study agent

Axitinib (AG013736; Inlyta) is a small molecule with the molecular formula C₂₂H₁₈N₄OS. It has a molecular mass of 386.469 g/mol. The chemical name of axitinib is *N*-Methyl-2-[[3-[(*E*)-2-pyridin-2-ylethenyl]-1*H*-indazol-6-yl]sulfanyl]benzamide

7.1 Drug supply

Axitinib will be supplied as 5mg and 1mg tabs by Pfizer, Inc.

7.2 Characterization of the Investigational medicinal product

Axitinib is available in red film-coated tablet form in 1mg and 5mg formulations. Patients will initially be given a 28-day supply of 5mg tablets (#56) and a 14-day supply of 1mg tablets (#28) to allow for easy dose titration or reduction during the initial cycle. For subsequent cycles, a sufficient quantity of 5mg and 1 mg tablets will be dispensed to allow for dose titration based on section 5.

Axitinib will be administered orally BID at approximately the same time in the morning and evening on a continuous dosing schedule, ie, without a break in dosing in the absence of drug-related toxicity. Axitinib tablets are to be taken approximately 12 hours apart and may be administered without regard to meals. Tablets must not be crushed, split, or dissolved, and patients should be instructed to swallow the study medication whole without manipulation or chewing of the medication prior to swallowing. A diary sheet will be provided to the patients to provide guidance for the correct use of axitinib (Section 15.5).

Patients must be instructed that if they miss a dose or vomit any time after taking a dose, they must not "make it up" with an extra dose, but instead resume subsequent doses as prescribed. Any missed dose may be taken late, up to 3 hours before the next scheduled dose of that day, otherwise, it should be skipped and dosing resumed with subsequent doses as prescribed. Patient must be instructed to record all doses (missed or vomited doses or extra doses) in a dosing diary supplied by the site. If doses are missed or vomited, this must be indicated in the source documents and CRFs.

****ALL drug diary sheets must be submitted electronically (email) or faxed to [name] (email: [contact]; [contact] at the completion of each cycle of treatment.**

7.3 Packaging, labeling and dispatch of the Investigational medicinal product

Axitinib will be dispensed in opaque plastic bottles to protect the compounds from light. Axitinib is a hazardous drug (due to possible reproductive toxicity), and should be handled according to the recommended procedures described in the current edition of the American Society of Hospital Pharmacists (ASHP), Technical Assistance Bulletin on Handling Cytotoxic and Hazardous Drugs, American Hospital Formulary Service (AHFS) Drug Information (1999) and its references. Procedures described in each institution's

pharmacy or hospital standard operating procedure manual should be followed when handling hazardous drugs.

7.4 Stability and Storage

Axitinib must be stored at controlled room temperature of 20°C to 25°C (68°F to 77°F).

7.5 Accountability and Destruction of Investigational medicinal product

The Principal Investigator (or an authorized designee) at must maintain a careful record of the inventory of the Investigational medicinal product received using the Drug Accountability Form. The study drug will be destroyed as per site's destruction policies and documentation of study drug destruction will be provided to Cleveland Clinic.

7.6 Drug Administration

Study drug accountability records will be maintained at the site pharmacy and will be available for review by the study monitor during each monitoring visit and at the close out visit. All medication must be stored in a secure area under the proper storage requirements with access restricted to the site staff pharmacist or designee(s).

Patient returned medication should be retained on site for monitor verification prior to destruction as per the institution's policy.

8. MEASUREMENT OF DRUG EFFECT

8.1 Safety assessment

The adverse effects of the drug will be assessed starting at Cycle 1 Day 1 including adverse events, vital signs and by clinically significant changes in the laboratory evaluations and EKGs. Treatment-related AEs will be assessed for 30 days following discontinuation of study drug therapy or until initiation of subsequent treatment, however documentation for study related purposes is only required through C13D1.

Adverse events (AE) will use the descriptions and grading scales found in the revised NCI Common Terminology Criteria for Adverse Events (CTCAE). This study will utilize the CTCAE Version 4.03 for adverse event reporting.

8.2 Efficacy assessments

Patients must have measurable disease at screening and will be evaluated for response on the basis of RECIST criteria version 1.1 (Section 15.1). Tumor measurements using physical examination, spiral CT scan and/or MRI or other appropriate techniques deemed suitable by the investigator will be performed at screening within 28 days of patient registration and repeated every 8 weeks until disease progression. After baseline, bone scan only if indicative of metastatic disease at baseline or if clinical signs/symptoms develop. CT Chest-Abdomen-Pelvis will be done every 8 weeks based on C1D1 date regardless of the date of baseline scans. Following Cycle 13 Day 1 assessment, CT scans to be done every 12 weeks. Disease assessment with CT chest-abdomen-pelvis will continue every 8 weeks for patients continuing on treatment following disease progression (bone scans to be done per MD discretion). Scans can be done more frequently per MD discretion; these scans will be submitted on an unscheduled disease assessment CRF.

9. SAFETY AND REPORTING REQUIREMENTS

9.1 Adverse Event

An adverse event (AE) is any untoward medical occurrence in a clinical investigation subject administered a pharmaceutical product during the course of a study and which does not necessarily have to have a causal relationship with this treatment. An adverse event can therefore be any unfavorable and unintended sign (including an abnormal laboratory finding), symptom, or disease temporally associated with the use of an investigational product, whether or not considered related to the medicinal product.

Disease signs, symptoms, and/or laboratory abnormalities already existing prior to the use of the product are not considered AEs after administration of the study product unless they reoccur after the subject has recovered from the pre-existing condition or they represent an exacerbation in intensity or frequency.

A laboratory test abnormality considered clinically relevant (e.g. causing the subject to withdraw from the study, requiring treatment or causing apparent clinical manifestations) or judged relevant by the Investigator should be reported as an adverse event.

9.2 Adverse Event Documentation

Adverse events will use the descriptions and grading scales found in the revised NCI Common Terminology Criteria for Adverse Events (CTCAE). This study will utilize the CTCAE Version 4.03 for adverse event reporting (Section 15.4).

All treatment-related adverse events (AE) and serious adverse events (SAEs) will be followed from the time first dose of study drug is administered and documented until resolution. Following C13D1, documentation is not needed for study related purposes.

Treatment-unrelated SAEs and all AEs will be followed from the time the first dose of study drug is administered and documented for 30 days, until resolution, or until a new therapy is started (whichever comes first).

All AEs must be recorded on case report forms (CRFs) through C13D1. Documentation must be supported by an entry in the subject's file. Each event should be described in detail along with start and stop dates, severity, relationship to investigational product as judged by the Investigator, action taken and outcome.

9.3 Serious Adverse Event

A Serious Adverse Event or Reaction is any AE occurring at any dose that:

- Results in death
- Is life-threatening
- Requires inpatient hospitalization or prolongation of existing hospitalization
- Results in persistent or significant disability/incapacity
- Is a congenital anomaly / birth defect
- Is an important medical event that may not be immediately life threatening or result in death or hospitalization, but may jeopardize the subject and may require medical or surgical intervention to prevent one of the outcomes listed above (example: intensive treatment in an emergency room or at home for bronchospasm, convulsions that do not

result in hospitalization). Medical and scientific judgment should be exercised in deciding whether some events should be considered as serious because their quick reporting to the sponsor may be of interest for the overall conduct of the study.

Life-threatening: The term “life-threatening” in the definition of “serious” refers to an adverse event in which the subject was at risk of death at the time of the event. It does not refer to an adverse event that hypothetically might have caused death if it were more severe.

Hospitalization: Any adverse event leading to hospitalization or prolongation of hospitalization will be considered as Serious, UNLESS at least one of the following exceptions are met:

The admission is pre-planned (i.e., elective or scheduled surgery arranged prior to the start of the study or for prophylactic insertion of a gastric feeding tube).

OR

The admission is not associated with an adverse event (eg, social hospitalization for purposes of respite care).

However it should be noted that invasive treatment during any hospitalization may fulfill the criteria of ‘medically important’ and as such may be reportable as a serious adverse event dependent on clinical judgment. In addition where local regulatory authorities specifically require a more stringent definition, the local regulation takes precedent.

Disability means a substantial disruption of a person’s ability to conduct normal life’s functions.

Important medical event: Any adverse event may be considered serious because it may jeopardize the subject and may require intervention to prevent another serious condition.

Any death (regardless of cause) that occurs from the time of administration of the first dose of study therapy until 28 days after the final administration of the study drug, and any death occurring after this time that is judged at least possibly related to prior treatment with the study drug, will be promptly reported.

Adverse events should be documented and recorded at each visit using NCI CTCAE version 4.03 (section 15.4).

9.4 Reporting Serious Adverse Events

All serious adverse events (SAE) and other adverse events must be recorded on case report forms.

SAEs should be reported to Pfizer using the Pfizer SAE form and cover page. SAE's should also be reported internally to individual institutions IRB per local IRB reporting policies and reported to the lead study coordinator by -email to [name] at [contact] or fax to [contact].

Serious adverse events should be documented and recorded at each visit using NCI CTCAE version 4.03 (section 15.4).

Drug-related SAEs from the time the first dose of study drug is administered will be followed and reported until resolution.

Drug-unrelated SAEs from the time the first dose of study drug is administered continue to be followed and documented for 30 days following discontinuation of study drug administration, initiation of subsequent treatment, or resolution (whichever comes first).

9.5 Procedure for Expedited Reporting

Responsibility for Reporting Serious Adverse Events to Pfizer

Each participating site will be responsible for submitting SAE (Initial and/or Follow-up reports) to Pfizer using the Pfizer's SAE cover form. The initial SAE form must be faxed to Pfizer and Cleveland Clinic within 24 hrs after the site is made aware of the SAE.

Reporting Serious Adverse Events to Local Research Ethics Boards

Cleveland Clinic will notify all Investigators of all Serious Adverse Events that are reportable to regulatory authorities as reported to Pfizer. This includes all serious events that are unexpected and related to protocol treatment. Investigators must notify their institutional review boards (IRBs) and file the report with their Investigator Site File. Documentation that serious adverse events (SAEs) have been reported to IRBs must be kept on file at each participating site.

Documentation can be any of the following:

- letter from the IRB acknowledging receipt
- stamp from the IRB, signed and dated by IRB chair, acknowledging receipt
- letter demonstrating the SAE was sent to the board

All expedited serious adverse events occurring within a center should also be reported to local IRBs.

9.6 Follow up of Adverse Events and Serious Adverse Events

Drug-related SAEs will be followed until resolution.

Drug-unrelated SAEs will be followed for 30 days following discontinuation of study drug administration, initiation of subsequent treatment, or resolution (whichever comes first).

9.7 Relationship

For all AEs, relationship to study drug will be reported on the appropriate AE CRF page. The PI must judge whether the study drug caused or contributed to the AE in which case it is considered to be an ADR, and report it as either:

Related (definitely, probably or possibly): there is a reasonable possibility that the study drug caused or contributed to the AE; this conclusion may be supported by the following observations, though these are not required for the determination of relatedness:

- There is a plausible time sequence between onset of the AE and study drug administration;

- There is a plausible biological mechanism through which study drug may have caused or contributed to the AE;

Not related: It is highly unlikely or impossible that the study drug caused or contributed to the AE; this conclusion may be supported by the following observations, though these are not required for a determination of not related: an alternate etiology needs to be provided for the adverse event.

- another cause of the AE is evident and most plausible;
- the temporal sequence is inconsistent between the onset of the AE and study drug administration; a causal relationship is considered biologically implausible.

10. STATISTICAL ANALYSIS

10.1 Study design and justification for sample size

Study design: This is a single-arm, single-stage phase II study investigating the use of an individualized dosing regimen of axitinib in patients with metastatic renal cell carcinoma. The primary outcome for this study is progression-free survival (PFS), defined as the interval between the date a patient first receives axitinib and the date of death or confirmed progression according to RECIST criteria. Any patient alive and without known progression at the time of analysis will be censored as of the last date the patient can be confirmed to be progression-free. Secondary endpoints include overall survival, RECIST-based response, and adverse events defined and graded according to NCI CTCAE Version 4.03 criteria.

Sample size: 38 evaluable patients.

Justification for sample size: Based on prior studies patients treated with axitinib following anti PD-1 therapy for mRCC have a PFS of approximately 6.5 months.^{19, 20} The hypothesis of this study is that with appropriate dose titration based on toxicities patients will reach a more optimal drug dose to increase benefit while minimizing risk. As such, we anticipate an approximately 45% increase in median PFS from 6.5 months to 9.5 months, which is felt to represent a clinically-meaningful improvement. Assuming accrual is fairly

uniform and will take approximately 18-24 months, there will be a minimum of 12 additional months of follow-up once the last patient has entered, and that PFS follows an exponential distribution (which is reasonable based on what has been seen historically in advanced RCC), 38 eligible and evaluable patients will be needed to test the above hypothesis with $\geq 80\%$ power (based on a 1-sided MLE test with 10% type I error). Allowing for ineligible/unevaluable a total of 40 patients will be accrued.

A 20% rate of discontinuation due to toxicity will be considered unacceptable. If at any time $>2/10$, $>4/20$, or $>6/30$ patients need to be discontinued due to toxicity, consideration will be given to stopping the study. With these guidelines the likelihood of a boundary being crossed in the first 10 patients is 7% if the underlying risk is 10%, 32% if it is 20%, and 62% if the risk is 30%. The overall likelihoods of a boundary being crossed at some point are 10%, 53%, and 89%, respectively.

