It is also well established that because of limited pill sizes available for oral drugs, dose reductions and dose escalations on a fixed schedule cannot be fine-tuned to the same extent as for IV chemotherapy.¹² With the usual dose reductions for axitinib to 3 mg bid and then 2 mg BID patients receive 60% and 40% respectively of the starting dose level and some pts may be under dosed. Conversely with the standard dose escalation to 7 mg BID and then 10 mg BID patients receive 140% and 200% of the starting dose respectively and some patients may be overdosed and end up requiring dose reduction. In our proposed study, most dose escalations and reductions are by a rate of 1mg BID which allows for a more precise titration schema based on tolerance and will likely result in less dose-escalation toxicity given the slower rate of titration.

Rationale for Patient Population: This study will enroll patients with mRCC previously treated with immune checkpoint inhibitors of programmed death 1 (PD-1) and programmed death ligand 1 (PD-L1). Anti-PD-1 and anti-PD-L1 inhibitors have demonstrated efficacy in TKI-refractory and previously untreated mRCC patients¹³⁻¹⁶ and clinical trials with these compounds are being offered to patients with mRCC as first line therapeutic options.^{17, 18} There are currently no prospective data on the efficacy of axitinib in the post-PD-1/PD-L1 setting, and the available retrospective data are limited to relatively small populations and demonstrate a PFS of approximately 7 months.^{19, 20} Recruitment of large number of patients to a first-line individualized axitinib dosing trial would be challenging in the era of checkpoint inhibitors clinical trials, but a trial limited to the post-PD-1/PD-L1 setting would be beneficial

both to identify an improved method of axitinib administration in general and also to prospectively document efficacy after PD-1/PD-L1 inhibition.

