10.3 Statistical Analysis

Data analysis will primarily be descriptive in nature, although as discussed above the underlying hypothesis that axitinib titration can improve PFS will be tested using a MLE test. Categorical data, such as adverse events and response rate, will be summarized using proportions and frequencies. Continuous endpoints, such as dose information will be summarized using medians and ranges, and PFS and overall survival will be summarized using the Kaplan-Meier method.

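### Does quoting about 7 months in Section 1.4 and about 6.5 months in Section 10.1 undermine the PFS test?

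*Combined protocol and SAP*

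**What the plan says.** Section 10.1 takes its benchmark from references 19 and 20: "Based on prior studies patients treated with axitinib following anti PD-1 therapy for mRCC have a PFS of approximately 6.5 months". It then sets the target: "we anticipate an approximately 45% increase in median PFS from 6.5 months to 9.5 months". The test is one-sided ("based on a 1-sided MLE test with 10% type I error"). PFS is assumed exponential, accrual uniform over 18 to 24 months, and follow-up at least 12 months after the last entry. On these terms 38 evaluable patients are said to give at least 80% power.

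Section 10.3 calls the analysis mainly descriptive and names one test, pointing back to Section 10.1 for it: "the underlying hypothesis that axitinib titration can improve PFS will be tested using a MLE test".

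Section 1.4, in the paragraph justifying the patient population, cites the same two references and says that "the available retrospective data are limited to relatively small populations and demonstrate a PFS of approximately 7 months". No current section explains the difference. The summary of changes says only that the sample size fell to 38 on new efficacy data for axitinib in this setting.

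**The concern.** With no control arm, a claim of improved PFS is only as good as the historical value it is set against. The protocol gives that value twice, from the same sources, half a month apart. Half a month is one sixth of the targeted gain (0.5 / 3.0).

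If 7.0 were the right benchmark, a positive test against 6.5 would be weaker evidence than its 10% error rate suggests, and power against 9.5 months would fall below 80%. Estimated medians in a narrow band would beat 6.5 but not 7.0, and a critic could cite Section 1.4 against a positive result.

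**Working it through.** **Inputs.** From Section 10.1: null median 6.5 months, alternative 9.5 months, one-sided alpha 0.10 (z = 1.2816), N = 38, accrual A = 18 or 24 months, minimum follow-up 12 months, exponential PFS. From Section 1.4: 7 months. The plan does not name the scale of its MLE test. The log scale is assumed below, with other scales shown as a range. Paired results are for A = 18 / 24.

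**Formulas.** With L = ln 2 / median:

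- P(event) = 1 − [exp(−12L) − exp(−(A+12)L)] / (A·L)
- P(reject) = Φ{[ln(m1/m0) − z/√(38·p0)]·√(38·p1)}, where m0 is the null median, m1 the true median, and p0, p1 their event probabilities
- Rejection cut-off for the estimated median = m0·exp(z/√(38·p0))

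**Event probabilities and expected events.**

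| Median (months) | P(event) | Events among 38 |
|---|---|---|
| 6.5 | 0.876 / 0.900 | 33.3 / 34.2 |
| 7.0 | 0.858 / 0.884 | 32.6 / 33.6 |
| 9.5 | 0.768 / 0.803 | 29.2 / 30.5 |

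**Step 1: the plan's own figure.** The ratio 9.5/6.5 = 1.46 agrees with the stated increase of about 45%. For A = 18, ln(9.5/6.5) = 0.3795 and 1.2816/√33.3 = 0.2221. Then (0.3795 − 0.2221) × √29.2 = 0.850, and Φ(0.850) = 0.802. For A = 24 the result is 0.812. The smallest N for 80% power is 37 to 38 on the log scale, 35 to 37 on the median scale and 38 to 39 on the cube-root scale. The 38 is reproduced from 6.5 v 9.5.

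**Step 2: could 38 have come from 7.0 v 9.5?** ln(9.5/7.0) = 0.3054 and 1.2816/√32.6 = 0.2245, so (0.3054 − 0.2245) × √29.2 = 0.437 and power is 0.669 / 0.679 (61% to 71% across scales). Reaching 80% would take 55 to 64 patients. So 38 does not come from that pair. If the ratio of 1.46 is kept instead (7.0 × 1.46, about 10.2 months), power is 0.795 / 0.806. The loss therefore comes from shrinking the targeted effect, not from the benchmark itself.

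**Step 3: what if the true benchmark is higher and titration adds nothing?** For a true 7.0, ln(7.0/6.5) = 0.0741, so (0.0741 − 0.2221) × √32.6 = −0.845 and Φ = 0.199 (0.200 for A = 24). Other scales give 17.7% to 22.2%. Simulating the log-scale Wald test gives about 18%. For a true 6.75 the approximation gives 14.5% and simulation about 13%. The same simulations put the size at a true 6.5 at 8.5% to 8.7%, so the approximation runs slightly high throughout.

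**Step 4: the disputed band.** The cut-off is 8.12 / 8.09 months for a null of 6.5 and 8.76 / 8.73 for a null of 7.0. The share of simulated trials positive against 6.5 but negative against 7.0 is about 14% if the true median is 9.5, 17% if it is 8.4 and 9% if it is 7.0.

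**The case for a change.** The strongest case for acting is that the mismatch touches the null of the only test. Section 10.1 works to the half-month, Section 1.4 admits that the data come from small series, and the remedy costs a sentence. If 7 is a rounding, one clause settles it. If it is not, the stated error rate flatters the result.

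What stands is that the two sections differ without explanation, that a reader may ask how 6.5 was derived, and that the conditional figures above are correct.

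The step from there to a flaw in the plan does not stand. Section 1.4 sets no hypothesis and does not say that its figure is a median. Section 10.1 uses 6.5 both as the historical value and as the start of the hypothesised increase, and Section 10.3 points to that text. An analyst following the plan would not test against 7. The 10% error rate is defined at 6.5. The 18% to 20% describes a different truth, and whether it applies turns on two references whose results the documents do not reproduce. Uncertainty about a historical control comes with any single-arm design. Making two sentences agree would not remove it.

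**Conclusion.** No change to the plan follows. The difference is a loose background figure, most simply read as 6.5 rounded to a whole month, although the documents do not say so. The test value is unambiguous at 6.5 months, and the 38 patients with roughly 80% power reproduce from it. Moving the null to 7.0 would need evidence from outside the documents. Harmonising the wording, adding a sensitivity sentence or reporting a confidence bound would leave the planned test and its result unchanged.

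The size of the issue, for anyone reading the result: if the historical median were really 7.0 and titration added nothing, the test would be positive about 18% (simulation) to 20% (normal approximation) of the time. An estimated median between about 8.1 and 8.8 months would beat 6.5 but not 7.0. These figures assume exponential PFS, 38 patients, uniform accrual over 18 to 24 months, 12 months' minimum follow-up and a log-scale MLE test.
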